#### 7.2.2 Sample size survey second part

The sample size is based on the original SOSAS study protocol (7). A randomly selection of 1873 households will provide sufficient power to all of the six arms of the Prevalence Study on Surgical Conditions 2019. For the current power calculation we have applied the original estimated prevalence of 7.3% surgical morbidity as used by Groen et al (33). We are aware that the original SOSAS study revealed that of the 3,645 respondents, 1,352 (37%; 95% CI 34·8–39·4) people indicated that they had a wound, burn, mass, growth, deformity, or other surgical condition at the time of interview and 896 (25%; 22·9–26·2) indicated that they needed surgical care (7). This found prevalence is much higher than the prevalence used originally for the power calculation. Hereby it might seem that we are over calculating the needed power if we use the 7.3% estimated prevalence.

However, as we are repeating the SOSAS study from 2012, we have chosen to use the original prevalence of 7.3% for surgical conditions in order to be able to compare our outcomes with the original study without the need to adjust for different sample sizes afterwards. Furthermore, this current SOSAS repeat study has additional arms on LUTS, severe wounds and maternal and perinatal health. The estimated prevalence for these conditions are  $\pm$  6%,  $\pm$ 1.9% and 2%

respectively (15, 40). As we are anticipating for lower prevalence of morbidity within three of the six sub-study arms we have calculated that an overall estimated prevalence of 7.3% will provide the needed power for all the arms within this study.

The sample size calculation is based on: Kelsey 1996 'Methods in observational Epidemiology' (43). The estimated proportion of the prevalence (p) of a surgical condition is set at 7.3%. The prevalence of 7.3% is based on a pilot study of the original SOSAS research group (44). The accepted range (L) around the estimated prevalence of the disorder is set at 1%. Letter Z is Cl (95%–Z is 1.96). In the pilot study from August 2011, 95% of the targeted population was eligible, and the same proportion responded (44). This provides a response rate (95%) and eligible rate (95%) needed for the sample size correction. The sample size is further corrected for the population size and is multiplied by a design-effect (DEFF) of 1.3, assuming that surgical conditions are not very clustered. The estimated population of Sierra Leone was 7,09 million in in 2015 (8)

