#### 7.2.1. Sampling method for the clusters

Sierra Leone is divided in four provinces, further divided into 16 districts, and 190 chiefdoms, which are further divided into 9,671 enumeration areas, the smallest administrative units in Sierra Leone. Sampling will be done through a weighted random cluster design, where the probability of cluster choice is proportional to the population size. From this moment onwards, a cluster and an enumeration area are the same. For Sierra Leone, the clusters will be randomly chosen in a two-stage sampling process starting with the Chiefdoms and selecting the number of clusters needed out of the Chiefdoms proportional to the population size in the chiefdoms to further select, the Enumerator Areas (EA's) out of the Chiefdoms. This process of sampling will be led by Statistics Sierra Leone, who will also provide maps and coordinates for the assigned clusters.

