#### 7.2.2. Assignment of the households within the cluster

If maps of structures of the randomly selected EAs are available, those are used for randomly designing the first household to approach. Thereafter every fifth structure at the right side of the interviewed household while standing with the back to the front door is approached for the survey. In case of more households per structure an on-site listing is made and random assignment of the household is facilitated by the use of the random calculator (that will be available on the tablet). If maps of structures are not available or out-dated an onsite structure count is made and random assignment of structures is given, by utilizing a random calculator.

To be able to have a weighted cluster sample, each cluster should have the same household numbers interviewed. Therefore, if a structure randomly chosen appears to be empty or the household does not give informed consent the next structure will be approached to be interviewed. Records will be kept on households' and individuals' refusal to participate, for the analysis of the results.

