#### 7.2.3. Sampling of the individuals for the six arms

There are six different arms in the prevalence 2019 study. Three arms have a similar selection model and three arms only include household members under certain conditions.

3xarm (SOSAS Repeat, Hernia, Wounds) = Two randomly selected household members

1xarm (LUTS)	= Only men over the age of 12 years
1xarm (Maternal)	= Only female(s) >12 years < 50 years
1xarm (Surgical Volume)	= All household members that had a surgical procedure in the last year

Inclusion of the household individuals will be according to the 'rolling the dice once rule'. Sampling of the two individuals out of the 1,873 households starts after the determination of the household size. A random number calculator will assign two household members to be surveyed. We have chosen not to include a minimum age, as this will not give a good demographic comparison with the District Health System (DHS). If one of the selected household members is under the age of 12 years, that person needs a chaperone to assist. This can be any of the present and available household members over the age of 18 years. The two selected individuals receive the SOSAS Repeat questionnaire including additional questions on groin hernia and wounds. If a randomly selected male is > 12 years of age, he will receive the additional LUTS questionnaire. If the selected household members are no men or men less than 12 years of age, in that household no additional LUTS questionnaire will be used. If a randomly selected individual is a female >12 years <50 years she will receive the additional Maternal and Perinatal health questionnaire. Additionally, the household representative will receive questions about all of the household members that had a surgical operation in the last year. These questions may be about the two randomly selected household members and/or for any additional persons residing within the ménage that underwent surgery in the last year.

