If a person is selected but not available for the interview, an appointment is made for later that day or the following day (each cluster has a minimum of two interview days). If by the third appointment the person is still not available, this person will be excluded from the analysis. When the (randomly assigned) household member does not provide consent no replacement is sought. If neither household member is available, or do not give consent, the next household will be approached to maintain the weighted sample size of households per cluster (e.g. ~25 households in each cluster).

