#### 7.3.5 Additional arm specific data collection: Surgical Volume

The household representative is the main person responsible for this part of the questionnaire. Due to the nature of the questionnaire, whereby the household representative will be interviewed first, the surgical volume related questions would come before the other arms. The household representative will be asked to provide an overview of the household members that have undergone a surgical procedure in the past year. This accounts for both major and minor procedures. Through this interview, also all household members who passed away after surgery will be identified.

When the household representative identifies a member of the household who underwent a major surgical procedure within the last year, the survey will be extended with additional questions to extracting in depth information concerning the procedure. These questions focus on the type of the surgical problem and the (type of) facility where the surgical procedure was performed. The household representative, and not the specific household member, will be responsible for completing this section of the questionnaire.

It would have been preferable to target the household member who underwent the surgical procedure but it is foreseen that a substantial part of the household members who underwent a surgical procedure in the past year will not be available for interview (e.g. work, travel). The original SOSAS study in Sierra Leone demonstrated that especially male household members are more prone to be absent during the data collection, creating a selection bias (7).

To comprehend if the household representative will be able to answer the in-depth questions reliably on behalf of the household member who had surgery, we will pre-test this approach. For validation purposes, all household members of the first 50 households that had undergone a major surgical procedure in the last year will be asked to fulfil the extended questionnaire themselves as well. The questionnaire will be presented to both the household member and the household representative separately and the answers will be compared in an internal analysis. We will use the found response difference for final analysis of all data. Furthermore, a response

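### Replacing empty, refusing or unavailable households to keep equal interviews per cluster does not keep selection probabilities equal, and the records planned would not show what the replacement did

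*Protocol*

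**What the plan says.** **Clusters and households.** Section 7.2.1 (Sampling method for the clusters) sets the first stage: "Sampling will be done through a weighted random cluster design, where the probability of cluster choice is proportional to the population size". Section 7.2.2 (Assignment of the households within the cluster) gives the reason for an equal take: "To be able to have a weighted cluster sample, each cluster should have the same household numbers interviewed". From this it derives the field rule that "if a structure randomly chosen appears to be empty or the household does not give informed consent the next structure will be approached". Section 7.2.3 adds a second replacement rule: "If neither household member is available, or do not give consent, the next household will be approached to maintain the weighted sample size". The target is about 25 households per cluster.

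**Individuals.** Section 7.2.3 treats people differently. A selected person who is absent is offered up to three appointments, and each cluster is worked for at least two days. A single member who refuses is not replaced. Within the household, "A random number calculator will assign two household members to be surveyed", after household size has been determined. The surgical volume arm instead covers all members.

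**Records and allowances.** Section 7.2.2 promises records of refusals by households and individuals. It does not mention empty structures or households that could not be reached. The second-part sample size already allows for loss: "This provides a response rate (95%) and eligible rate (95%) needed for the sample size correction". Section 7.2.1 (Sample size survey first part) adds a 5% margin for representatives who do not consent.

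**Known absence problem.** On the 2012 survey, Section 7.3.5 says that "especially male household members are more prone to be absent during the data collection, creating a selection bias".

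**The concern.** With clusters drawn in proportion to size, an equal number of households *selected* per cluster keeps household chances roughly level. Topping up to an equal number *interviewed* does not. A household next to a failed one gains a second route into the sample, and households that were missed are represented by households where someone was in. Section 3 defines membership by eating from the same pot and having slept there the night before, so people who are out by day belong to the target population.

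What is at stake is the national prevalence in every arm. Equal counts would make the fieldwork look complete, while the records could not show how many households had been swapped or why. The protocol itself reports that absence biased the 2012 survey with respect to men, and one of the added arms (LUTS) is for men only.

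A separate point concerns individuals. Two people are taken from every household whatever its size, so an equal household take does not give people equal chances.

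**Working it through.** **1. The plan's own figure.** Inputs from Section 7.2.2 (Sample size survey second part): p = 7.3%, L = 1%, design effect 1.3, response 95%, eligibility 95%.

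- 1.96² × 0.073 × 0.927 / 0.01² = 2,599.6
- 2,599.6 × 1.3 = 3,379.5
- 3,379.5 / 0.95 / 0.95 = 3,744.6, so 3,745 people
- 3,745 / 2 = 1,872.5, so 1,873 households; 1,873 / 75 = 24.97 per cluster

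The figure reproduces. The allowance for non-response and ineligibility is 3,745 − 3,380 = 365 people. Households that fail are then replaced as well. Their loss is made good twice in number, and its bias is left untouched.

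**2. The rules side by side.**

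| Event | Rule | Record promised |
|---|---|---|
| Structure appears empty | next structure; no revisit stated | none stated |
| Household refuses | next structure | yes |
| One selected member absent | up to three appointments, then excluded | none stated |
| One selected member refuses | not replaced | yes |
| Neither member available or consenting | next household | refusals only |

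The same event, nobody in when the team calls, leads to repeat appointments once a person has been drawn and to substitution if it happens at the door.

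**3. What substitution could do to an estimate.** Let f be the share of households replaced, and r their prevalence relative to households reached. Assume that substitutes resemble the average household reached. If true prevalence is P, the survey estimates P / [(1 − f) + f × r]. With P = 7.3%, the shift in percentage points is:

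| f | r = 0.5 | r = 1 | r = 1.5 |
|---|---|---|---|
| 5% | +0.19 | 0 | −0.18 |
| 10% | +0.38 | 0 | −0.35 |
| 20% | +0.81 | 0 | −0.66 |

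For example, 7.3 / (0.8 + 0.2 × 0.5) = 7.3 / 0.9 = 8.11. Both f and r are assumptions; the documents give neither. Leaving the gaps unfilled and unadjusted would give the same expected shift. The gain therefore comes from revisits, which lower f, and from records, which let f be seen.

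**4. Person-level probability in Part 2.** Take EA selection proportional to population M at face value. Let the EA have S structures, the structure h households and the household k members. With 25 structures visited, one household per structure and two people per household:

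- inclusion ∝ M × (25/S) × (1/h) × (2/k)

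Within a household, 2/k is 1.00 at k = 2, 0.50 at k = 4, 0.25 at k = 8 and 0.20 at k = 10. Two people in the same EA, in single-household structures, differ fourfold if their households have 2 and 8 members. This is arithmetic on the stated rule. It touches the SOSAS repeat, LUTS, hernia, wound and maternal arms, but not surgical volume.

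**5. The matching weight.** The inverse, up to a constant, is (S/M) × h × k / (number selected). The factor S/M cannot be left out. Take two EAs with equal M and equal k, and with h = 1 and h = 3. Then S = M/(k × h), so the full weight is [1/(k × h)] × h × k/2 = 1/2 in both, a 50/50 split. Using h × k/2 alone gives k/2 and 3k/2, a 25/75 split, which would itself bias the estimate.

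**The case against.** The strongest defence has four parts.

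- **An empty structure may be an uninhabited one**, and replacing that is harmless. This stands as far as it goes. But the protocol does not separate uninhabited from temporarily unoccupied, so enumerators may treat both alike.
- **The 95% rates concern individuals.** A single missing member is not replaced, so the inflation keeps a purpose. This also stands. The overlap is confined to households lost whole, and the 5% margin in the first part is expressly for representatives who do not consent, whose households are replaced too.
- **Safeguards exist.** Refusals are recorded, individuals are followed up, and a pilot will look at response, eligibility and the design factor. None of these reaches structures where nobody was in.
- **Household-size weighting may sit in a statistical analysis plan that is not shown**, and household size is known before selection. This is right, so the absence of a weighting formula is not a fault here. The protocol does not say that the analysis will be unweighted, and it makes no promise of equal probability for persons.

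Some stronger readings are tempting but not supported. A reader might infer that Part 1 answers are thrown away when a household is replaced; Section 7.2.3 does not say so, it is only silent. A reader might infer that taking "every fifth structure at the right side of the interviewed household" exhausts the EA; that step applies only where maps are available, structures per EA are not given, and selection in proportion to size favours larger EAs than the simple average. A reader might also add a weighting loss, computed from the overall spread of household size, to the 1.3. Selection in proportion to size with an equal take largely cancels the between-EA part, so that would overstate the loss.

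**Conclusion.** The concern holds in a limited form. The reason given in Section 7.2.2 for equal interviews does not justify substitution, the handling of absence is inconsistent between structures and people, and the promised records would not allow the effect to be examined. The documents do not give its size or direction. Under the assumed ranges in the working the shift is −0.7 to +0.8 points on 7.3%, close to the planned 1 point at the extremes and zero if replaced and reached households are alike.

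The unequal person probability in Part 2 is certain, but weights can correct it if the right counts are collected. It biases prevalence only if the analysis ignores it and the conditions vary with household size. Any variance cost beyond the design effect of 1.3 depends on the within-EA spread of household size, which the documents do not give, so no figure is offered.

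This is worth changing before fieldwork, because contact history that is not recorded in the field cannot be rebuilt.

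**What to change.** 1. Define an empty structure. Separate uninhabited structures, which may be replaced freely, from occupied ones whose members are out.
2. Revisit the latter within the existing stay of at least two days before any substitution.
3. Record every empty, unavailable and refusing structure or household, not refusals alone.
4. Flag each substitute and repeat the main estimates without substitutes. This shows whether they differ from the households first drawn; it does not recover those never reached.
5. State that Part 1 answers already given by a representative are kept when the selected members cannot be interviewed.
6. Record structures per EA and households per structure, and keep the EA population used for selection. Design weights can then be formed as (structures in the EA / EA population used for selection) × households per structure × household size / number selected.
7. Give the unweighted result alongside, so that the comparison with 2012 stays like for like.

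The cost is some revisits inside time already planned, a few extra fields on the tablet, and somewhat wider intervals from weighting.

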#### 7.2.3. Sampling of the individuals for the six arms

There are six different arms in the prevalence 2019 study. Three arms have a similar selection model and three arms only include household members under certain conditions.

3xarm (SOSAS Repeat, Hernia, Wounds) = Two randomly selected household members

1xarm (LUTS)	= Only men over the age of 12 years
1xarm (Maternal)	= Only female(s) >12 years < 50 years
1xarm (Surgical Volume)	= All household members that had a surgical procedure in the last year

Inclusion of the household individuals will be according to the 'rolling the dice once rule'. Sampling of the two individuals out of the 1,873 households starts after the determination of the household size. A random number calculator will assign two household members to be surveyed. We have chosen not to include a minimum age, as this will not give a good demographic comparison with the District Health System (DHS). If one of the selected household members is under the age of 12 years, that person needs a chaperone to assist. This can be any of the present and available household members over the age of 18 years. The two selected individuals receive the SOSAS Repeat questionnaire including additional questions on groin hernia and wounds. If a randomly selected male is > 12 years of age, he will receive the additional LUTS questionnaire. If the selected household members are no men or men less than 12 years of age, in that household no additional LUTS questionnaire will be used. If a randomly selected individual is a female >12 years <50 years she will receive the additional Maternal and Perinatal health questionnaire. Additionally, the household representative will receive questions about all of the household members that had a surgical operation in the last year. These questions may be about the two randomly selected household members and/or for any additional persons residing within the ménage that underwent surgery in the last year.

If a person is selected but not available for the interview, an appointment is made for later that day or the following day (each cluster has a minimum of two interview days). If by the third appointment the person is still not available, this person will be excluded from the analysis. When the (randomly assigned) household member does not provide consent no replacement is sought. If neither household member is available, or do not give consent, the next household will be approached to maintain the weighted sample size of households per cluster (e.g. ~25 households in each cluster).

#### 7.3. Data collection – SOSAS Repeat

The data will be collected via individual face-to-face interviews using a national communitybased sampling survey at the houses of the respondent. This fall the recruited students/nurses/medical staff will be trained to become enumerators. These enumerators will collect data with handheld tablets provided by the Prevalence 2019 research team. The recruited drivers will use a Global Positioning System to get the enumerators to the exact location and enumerators familiar with working with maps will be recruited.

#### The SOSAS repeat survey consists of two parts.

The first part is administered to a household representative to establish the number of household members, identify deaths in the household during the previous year, and establish whether any of the deceased household members had any of the following conditions in the week before their death: abdominal distension or pain; bleeding or illness during childbirth; injury; mass, growth, or swelling; acquired deformity; or a wound not due to injury or congenital deformity.

The second section consists of structured interviews of two randomly selected household members who undergo a head-to-toe verbal examination covering six anatomical regions: face, head, and neck; chest and breast; abdomen; groin, genitals, and buttocks; back; and arms and hands and legs and feet. The need for surgical care was recorded on the basis of an individual's response to whether they had a wound, burn, mass, deformity, or other condition needing surgical assessment or care—i.e., the respondent decided whether or not they felt they needed surgical care. A surgical procedure was defined as: wound care, suturing, incision, excision, or other manipulation of tissue, in a safe and painless way. Procedures were deemed major if they required regional or general anaesthesia and minor if they required local anaesthetics or none.

